#### (2) Device Defect

Device defect refers to the unreasonable risks that may endanger human health and life safety under normal use of medical devices in the course of clinical trials, such as label errors, quality problems, failures, etc. In the course of this clinical trial, if the use of devices fails due to device defects, the investigator shall conduct routine treatment according to clinical needs. The investigator should document all discovered device defects that occur during clinical trials.

#### (3) Definition of Serious Adverse Events

#### A. Definition of serious adverse events

Serious adverse events refer to those that occur during clinical trials of medical devices resulting in death or serious deterioration of health. Including fatal diseases or injuries, permanent defects in body structure or body function, the need for hospitalization or prolonged hospitalization, the need to take medical measures to avoid permanent defects in body structure or body function: events leading to fetal distress, fetal death or congenital abnormalities, birth defects, etc., during screening or follow-up, Prospective or elective surgery performed by subjects was not recorded as a serious adverse event.

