#### 2. Experimental Method

According to the Guiding Principles for Clinical Trial Design of Medical Devices, a prospective, multicenter, randomized, single-blind, parallel-controlled clinical trial was designed, and the comparison type was non-inferior design.

**Randomization Method:** Subjects will be enrolled in this clinical trial after signing informed consent and meeting the inclusion criteria but not the exclusion criteria. The sample size and block length were set using the system generation or a seed number specified by the randomizer. The random number table required for the test was generated by the PROC PLAN process, and the random number table was introduced into the random system. According to the random system grouping, the subjects were randomly assigned to the experimental group or the control group, and the ratio of the experimental group and the control group was 1:1.

**Masking (Single):** The researchers can visually distinguish the experiment products and the control products, so the researchers cannot be blinded and the participants were blinded.

**Non-Inferior Design:** The control product is a marketed device whose efficacy/safety has been recognized, so the non-inferior design is used. If the difference in efficacy/safety between the test device and the control device is less than the pre-set non-inferiority threshold, the difference is within the clinically acceptable range.

Selection of Reference Products: At present, there is no biological bone hollow screw with the same principle and material in China. According to the Guiding Principles for Clinical Trial Design of Medical Devices, priority should be given to commercially available similar products whose efficacy and safety have been clinically recognized when selecting positive controls. And if reasonable reasons cannot be used for similar products already on the market, a product as similar as possible can be used as a positive control. Therefore, the absorbable screw (Inion Freedom Screw) developed by Inion Oy, Finland, was selected as the control product in this clinical trial.

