# 4. The Diagnosis and Treatment Methods of Experimental and Control Medical Devices

#### 4.1 Instructions for the Installation and Use of Experimental Devices

According to the specific conditions of each patient, the selection of the appropriate model and size of the implant is an important factor affecting the success rate of surgery. After implantation, the implant will be in a repetitive stress environment for a long time, so attention must be paid to patient selection, proper placement of the implant, postoperative care and functional rehabilitation to minimize the stress on the implant, otherwise such stress may lead to material fatigue and subsequent fracture, bending or loosening of the implant before bone healing is achieved. This can cause damage or require early removal of the implant.

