#### 4.4 After Surgery

(1) The physician should provide the patient with a detailed description of the limitations of the product. Patients should be warned that complications such as bending, loosening or breaking of the implant may be caused by excessive weight bearing, excessive muscle activity or sudden impact on the surgical site. Patients should be told how to limit and control physical activity and advised to avoid strenuous exercise and excessive weight bearing.

(2) During the healing stage of the fracture, the physician should advise the patient not to smoke or drink too much alcohol.

(3) It is very important to confirm whether bone healing occurs after the

operation by X-ray. Bone non-union or delayed healing during the treatment stage will cause the implant to be subjected to repeated stress for a long time, which may fatigue the product and eventually bend, loosen or fracture. Therefore, if non-healing occurs or if the implant is loose, bent or broken, the implant should be adjusted or removed when serious damage is imminent.

(4) Any removed implants should be properly disposed of to ensure that the product will not be used in other surgeries.

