# Requirements for Reporting Adverse Events and Device Defects

#### (1) Definition and Reporting of Adverse Events

#### A. Definition of adverse events

Adverse events refer to adverse medical events that occur during clinical trials of medical devices, whether or not they are related to the experimental medical devices. Adverse events were recorded from device use.

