B. Unqualified Criteria: If the clinical healing rate of fracture is different between the test product and the control product 24 weeks after surgery (experimental group-control group)95%CI lower limit $\leq -10\%$, the clinical validation can be considered to have failed.

6. Criteria and Reasons for Terminating the Trial on Statistics

Not applicable

7. Statistical Methods for All Data, Along With Treatment of Missing, Unused, or Erroneous Data (Including Dropouts and Withdrawals) and Unreasonable Data.

A. Characteristics of the cases

Enrollment and completion: The number of enrolled and completed cases was summarized, and the list of dropped cases was listed.

General information and baseline characteristics: Demographic information and other disease history of the subjects were statistically described.

According to the numerical characteristics of the variables, T-test/corrected T-test was used to compare the age, blood pressure and other quantitative data of the two groups of subjects. Chi-square test/exact probability method was used to compare the qualitative variables such as gender and past medical history of the subjects between the groups. The Wilcoxon rank sum test was used to compare the ordered

classified data between groups.

Baseline: Baseline is defined as the basic situation of the subject before clinical operation.

B. Analysis of effectiveness evaluation indicators

Analysis of main evaluation indicators: The main evaluation index was the clinical healing rate of fracture at 24 weeks after surgery, and the difference of 95% confidence interval between the experimental group and the control group was calculated.

Analysis of secondary evaluation indicators: clinical healing rate of fractures and performance indicators of pain scoring instruments at 12, 48 and 72 weeks after surgery were statistically described by descriptive methods of qualitative or quantitative data according to the characteristics of variable types, and comparison between groups was performed by Chi-square test/exact probability /t test.

C. Analysis of security indicators

The occurrence of adverse events was clinically observed, event name, start time, end time, severity, corrective treatment, and relationship with the experimental product were recorded, and the incidence of adverse events was calculated and compared between groups. Study discontinuation due to adverse events and the occurrence of serious adverse events should be specifically noted.

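### The SAE definition exempts undefined 'prospective or elective' surgery during follow-up, so a scheduled removal or revision of the study screw could be left out of the SAE count

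*Protocol*

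**What the plan says.** The protocol defines SAEs under Requirements for Reporting Adverse Events and Device Defects, (3) A. Among the consequences that make an event serious it lists "the need for hospitalization or prolonged hospitalization, the need to take medical measures to avoid permanent defects in body structure or body function". The same sentence closes with the exemption: "during screening or follow-up, Prospective or elective surgery performed by subjects was not recorded as a serious adverse event". Part B of that section requires the investigator to report an SAE within 24 hours to the sponsor, the institution's trial management department and the ethics committee.

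Two other sections foresee further surgery on the implant. Section 4.1 says of fatigue, bending or loosening before the bone heals: "This can cause damage or require early removal of the implant". Section 4.4, item 3, says that "if non-healing occurs or if the implant is loose, bent or broken, the implant should be adjusted or removed when serious damage is imminent".

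Other records exist alongside the SAE rule. Adverse events are defined as recordable "whether or not they are related to the experimental medical devices", and the device-defect section says: "The investigator should document all discovered device defects that occur during clinical trials". SAP section 7C plans a between-group comparison of adverse event incidence and adds: "Study discontinuation due to adverse events and the occurrence of serious adverse events should be specifically noted".

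**The concern.** An exemption for planned surgery usually serves to keep operations that have nothing to do with the trial from being counted as harms. This one has no such boundary. It explicitly covers follow-up, which section 5.7 sets at 18 months after surgery, and that is when an operation on a failed study screw would take place.

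A repeat operation on the study fracture is among the more informative safety events in a trial of a fixation device. If sites apply the clause to such operations, the SAE listing becomes incomplete and the expedited report is not triggered. If sites apply it differently, SAE counts lose comparability across the six centres. Protocol section 2 says that "the researchers cannot be blinded and the participants were blinded", so whoever classifies an operation at the site is likely to know the assigned screw, and the omission could differ by arm.

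**Working it through.** The plan gives no figure on this point, so the check is a comparison of texts.

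**1. How far does the exemption reach?** The clause names two kinds of surgery and two periods. It contains no date limit (such as planned before consent), no condition limit (such as unrelated to the fracture) and no exception for the study site. Neither document defines the two terms.

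**2. Can *elective* include surgery on the study fracture?** Protocol section 2.1 (Screening Period) uses the word for subjects awaiting their trial operation: if that surgery is elective, the investigator decides whether to repeat preoperative tests that have become too old. There the word describes scheduling. It does not mean unrelated to the fracture. A booked removal or revision of the study screw fits that usage.

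**3. Are such operations foreseen?** Yes, in sections 4.1 and 4.4. Section 4.4 ties adjustment or removal to imminent serious damage and does not call it elective. Section 4.1 has no such qualifier.

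**4. Does the exemption conflict with the criteria before it?** It can. Where admission for the operation is what makes a failed fixation serious, exempting the operation can remove the criterion that was met. The definition does not say which part prevails.

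**5. What still captures the event if the operation is not an SAE?**

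| Record | What remains | What is missing |
|---|---|---|
| Adverse event (protocol, AE definition and 7.2.3; SAP 7C) | The underlying event, with severity, corrective treatment and relationship to the product | No 24-hour report. The *severe* grade requires danger to life, death, disability or immediate emergency care, so a scheduled revision would probably be graded lower |
| Device defect (protocol, device-defect section; visits V0 to V7) | A defect or failure of the screw | The SAP plans no analysis of defects, and non-union without a defect would not appear |
| Healing (protocol 6.1) | Healed or not at 12, 24, 48 and 72 weeks | Whether the subject was operated on again |
| Safety parameters (protocol 7.1) | Vital signs, laboratory tests, adverse events | Reoperation is not named |

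The event therefore leaves traces in several places, but no planned output counts reoperations by arm.

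**The case against.** The strongest reply is that the clause exempts the surgery and not the event that led to it. Non-union, loosening or breakage that needs hospital treatment, or intervention to avoid permanent impairment, still meets the criteria earlier in the same sentence. Section 4.4 describes removal under imminent serious damage, which is hard to call elective. The clause also reads like a rough translation, and *prospective* may mean surgery already planned at entry, although the text does not say so. This stands to the extent that the omission is possible and not certain.

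A reader might go further and infer that the rule conceals any excess of device failure with the test screw. The documents do not support that. Fracture healing is the primary endpoint and is assessed at three other visits as well. Adverse events are recorded at every postoperative visit whether or not they are related to the device, with their corrective treatment. Device defects are recorded at every visit. The planned between-group comparison in SAP 7C is of adverse event incidence, while SAEs are only to be noted specifically, so the underlying event would stay in that comparison.

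That unblinded investigators would decide what counts as elective is also an inference. The protocol makes them responsible for reporting SAEs but does not say who makes this classification.

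None of this settles how a scheduled operation on the study screw is to be recorded. The other records do not replace the SAE report or a count of reoperations.

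**Conclusion.** The point holds as a defect in a reporting definition. As written, the exemption is unlimited and can conflict with the seriousness criteria in its own sentence. A scheduled removal or revision of the study screw *could* be left out of the SAE count and the 24-hour report. That rests on a literal reading of *elective*, which the protocol's own use of the word in section 2.1 supports.

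It would be too strong to say that such operations *will* go uncounted, because the underlying event remains recordable and may itself be reported as an SAE.

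No size can be attached. It might be tempting to turn the SAP's assumed non-healing rate into a number of missed SAEs, but 24-week non-healing is not the same as being a candidate for reoperation. Under section 6.2.1, residual tenderness or incomplete bridging on X-ray is enough to be classed as not healed, and healing is assessed again at 48 and 72 weeks. The documents give neither a reoperation rate nor the share of reoperations that would be scheduled.

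The change is worth making because the remedy is small and the events concerned bear directly on device safety.

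**What to change.** 1. In the SAE definition, limit the exemption to surgery planned before informed consent for a condition unrelated to the study fracture or device.
2. State that any reoperation at the study fracture site (removal, adjustment, revision or re-fixation), and the event leading to it, is assessed against the SAE criteria whether or not it was scheduled.
3. Reconcile protocol section 4.4, item 3, with the SAE definition, so that it is clear how an adjustment or removal foreseen there is recorded.
4. Add to SAP section 7C a table of study-site reoperations by arm.

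These changes concern recording and reporting only. They do not alter when or whether an implant is removed. The cost is a short protocol amendment, one safety table, and a slightly higher SAE count and reporting load.

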#### **B.** Serious adverse event reporting process

If a serious adverse event occurs in a clinical trial, the investigator shall immediately take appropriate treatment measures for the subject; meanwhile, the investigator shall report the serious adverse event to the sponsor, the management department of the medical device clinical trial institution, and the ethics committee within 24 hours after learning about it; Serious adverse events were followed up in accordance with the provisions of the clinical trial protocol, and serious adverse event follow-up reports were submitted.

# **Direct Access to Source Data and Files**

Clinical trial institutions and investigators should allow trial-related monitoring, verification, ethics committee, and regulatory inspections with direct access to source data/documents.

Protocol Number: XG2114

Statistical Analysis Plan

A Clinical Study to Evaluate the Safety and Efficacy of Biologic Hollow Bone Screws

Name of Experimental Medical Device: Biologic Hollow Bone Screws

Clinical Trial Institution: The First Affiliated Hospital of PLA Air Force Medical University

The Sponsor: Jiangxi Sike Biotechnology, China

Collaborative Research Organization: Nanjing Sigma Medical Technology Co., LTD

NCT Number:

Document Date: January 21, 2024

Statistical Analysis

1. Statistical Design

A prospective, multicenter, randomized, single-blind, parallel-controlled clinical trial was conducted. The comparison type was non-inferiority design.

2. Analytical Methods

95% confidence interval method was used for the main efficacy indicators, and bilateral tests were used for all statistical tests, and $P \leq 0.05$ was considered to be statistically significant.

The description of quantitative indicators will calculate the mean, standard deviation, median, minimum, maximum. The classification index is described by the number of cases and percentage of each type. Statistical analysis was performed using SAS 9.4 software.

3. Calculation of Sample Size

A. Total sample size

With reference to the Guiding Principles for the Technical Review of Product Registration of Metal intramedullary nail System and the Guiding Principles for the Technical Review of Product Registration of Metal bone plate internal fixation System, the clinical healing rate of fractures at 24 weeks after surgery was used as the main therapeutic evaluation index to calculate the sample size.

According to the references, it is assumed that the clinical healing

rate of fracture PC at 24 weeks after operation of the control product is about 95.5%. The clinical fracture healing rate PT of the test product is expected to be comparable to that of the control product, according to the non-inferiority sample size formula:

$$n_T = n_C = \frac{(Z_{1-\alpha/2} + Z_{1-\beta})^2 [P_C(1-P_C) + P_T(1-P_T)]}{(|D| - \Delta)^2}$$

P_T and P_C were the expected event rates of the experimental group and the control group, respectively. $|D|$ is the absolute value of the difference between the expected rates of the two groups, $|D|=|P_T - P_C|$. Δ is the non-inferiority margin value, which is -10%. The type I error was $\alpha=0.05$ (two-sided) and the type II error was $\beta=0.20$. There were 68 patients in each group, and a total of 136 patients in the two groups. Considering the dropout rate and block length, 160 cases were included in the experimental group and the control group, and the number of subjects in the experimental group and the control group was 1:1.

B. Number of clinical trials for each disease and reasons for their determination

According to the scope of application of the test instruments, subjects who meet the inclusion criteria and fail to meet the exclusion criteria will be strictly screened in this study. According to the statistical distribution, subjects with different diseases will be distributed in the experimental group and the control group, and the specific diseases will

no longer be restricted.

C. Minimum and maximum number of subjects and reasons for each clinical trial facility in multicenter clinical trials

This trial is expected to be conducted simultaneously in 6 clinical trial institutions, and in principle, the number of enrolled centers will be evenly distributed as far as possible to ensure adequate center representation. However, considering the feasibility and enrollment progress, the number of centers and the number of subjects in the centers will be adjusted according to the actual situation, so as to ensure that the enrollment scale of each center is relatively balanced, and the final enrollment scale of a particular center should not exceed 50% of the total number of cases.

3. The Significance Level and Degree of Assurance of Clinical Trials

A. Significance level: 0.05

B. Degree of confidence: 0.8

4. Expected Drop-out Rate

The expected shedding rate of this clinical trial is $\leq 15\%$.

5. Qualified/Unqualified Criteria for Clinical Trial Results

A. Eligibility Criteria: If the clinical healing rate of the experimental product is worse than that of the control product at 24 weeks after surgery (test group-control group) by 95%CI lower limit $> -10\%$, then the experimental product is not inferior to the control product, and the

clinical verification can be considered successful.

B. Unqualified Criteria: If the clinical healing rate of fracture is different between the test product and the control product 24 weeks after surgery (experimental group-control group)95%CI lower limit $\leq -10\%$, the clinical validation can be considered to have failed.

6. Criteria and Reasons for Terminating the Trial on Statistics

Not applicable

7. Statistical Methods for All Data, Along With Treatment of Missing, Unused, or Erroneous Data (Including Dropouts and Withdrawals) and Unreasonable Data.

A. Characteristics of the cases

Enrollment and completion: The number of enrolled and completed cases was summarized, and the list of dropped cases was listed.

General information and baseline characteristics: Demographic information and other disease history of the subjects were statistically described.

According to the numerical characteristics of the variables, T-test/corrected T-test was used to compare the age, blood pressure and other quantitative data of the two groups of subjects. Chi-square test/exact probability method was used to compare the qualitative variables such as gender and past medical history of the subjects between the groups. The Wilcoxon rank sum test was used to compare the ordered

classified data between groups.

Baseline: Baseline is defined as the basic situation of the subject before clinical operation.

B. Analysis of effectiveness evaluation indicators

Analysis of main evaluation indicators: The main evaluation index was the clinical healing rate of fracture at 24 weeks after surgery, and the difference of 95% confidence interval between the experimental group and the control group was calculated.

Analysis of secondary evaluation indicators: clinical healing rate of fractures and performance indicators of pain scoring instruments at 12, 48 and 72 weeks after surgery were statistically described by descriptive methods of qualitative or quantitative data according to the characteristics of variable types, and comparison between groups was performed by Chi-square test/exact probability /t test.

C. Analysis of security indicators

The occurrence of adverse events was clinically observed, event name, start time, end time, severity, corrective treatment, and relationship with the experimental product were recorded, and the incidence of adverse events was calculated and compared between groups. Study discontinuation due to adverse events and the occurrence of serious adverse events should be specifically noted.

For various safety indicators such as vital signs and laboratory tests,

T-test/corrected T-test /Wilcoxon rank sum test were used for comparison between groups according to the numerical characteristics of variables; Chi-square test/exact probability method was used for comparison between groups for qualitative data; Wilcoxon rank sum test or CMH chi square test was used for ordered classified data.

8. Procedures for Deviation from the Original Statistical Plan

The implementation shall be strictly in accordance with the requirements stipulated in 7. If other statistical methods not specified in the program are needed, an application shall be submitted to the Ethics committee for approval before implementation.

9. Selection Criteria and Reasons for Subjects Included in the Analysis

Full Analysis Set (FAS) is a set of subjects that are as close as possible to the ideal in line with the principles of intentionality. The data set is derived from the elimination of subjects from all enrolled subjects by a minimum and reasonable method.

Per Protocol Set (PPS), Also known as a valid case, valid sample, or evaluable case sample. It is a dataset generated from a subset of cases that are fully compliant with the trial protocol and is a subset of the total analysis set. Adherence includes considerations such as the treatment received, the feasibility of the main measure, and the absence of significant violations of the protocol.

Safety Analysis Set (SS): When performing a safety evaluation, the set of subjects used for aggregation is called a safety analysis set. The safety data set shall include all subjects who have used this tester.

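### The SAP never names the 95% interval that decides non-inferiority, and at 68 per arm none of four common intervals gives both 80% power and 2.5% one-sided error

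*SAP*

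**What the plan says.** SAP 1 sets the comparison: "The comparison type was non-inferiority design". SAP 5 gives a single success rule: if the lower 95% limit for the difference (test minus control) lies above -10%, "then the experimental product is not inferior to the control product"; otherwise the trial fails.

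The interval is described in two places. SAP 2, in wording shared with the protocol's Statistical Analysis section, says "95% confidence interval method was used for the main efficacy indicators". SAP 7B says "the difference of 95% confidence interval between the experimental group and the control group was calculated". Neither gives a type. SAS 9.4 is named, but no procedure or option for this interval. By contrast, SAP 7 does name tests for the baseline, secondary and safety comparisons.

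On size, SAP 3A uses an unpooled normal-approximation formula with about 95.5% healing on control, a comparable test rate, a margin of -10%, two-sided alpha 0.05 and beta 0.20, and concludes: "There were 68 patients in each group, and a total of 136 patients in the two groups". The later section on significance level repeats the power ("Degree of confidence: 0.8"). SAP 4 adds the allowance for loss: "The expected shedding rate of this clinical trial is" at most 15%. Enrolment is 160, 80 per arm. SAP 8 makes section 7 binding: "The implementation shall be strictly in accordance with the requirements stipulated in 7".

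**The concern.** When only about three subjects per arm are expected not to heal, the standard 95% intervals for a difference in proportions no longer agree. Some are too short near 100% and let an inferior device through too often; others keep their error rate but need more subjects. A plan that says only that a 95% interval will be used therefore fixes neither the type I error nor the power of its one confirmatory test.

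Two things are at stake. If the interval is chosen after the data are seen, the choice can turn a failure into a success. If the interval suggested by the sample-size formula (Wald) is what the sponsor intends, the stated error level is not met. Either way, the 80% power and the 5% two-sided alpha do not both describe the trial at its planned evaluable size.

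**Working it through.** **Inputs.** Control rate 95.5%, test rate comparable (taken as 95.5%), margin -10 points, two-sided alpha 0.05, power 80% (SAP 3A); loss of up to 15% (SAP 4); rule: lower limit above -10% (SAP 5). A lower two-sided 95% limit implies 2.5% one-sided error.

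**Step 1: the plan's own figure.** n = (1.960 + 0.842)² × 2 × 0.955 × 0.045 / 0.10² = 67.46, rounded up to 68 per arm. Then 68 / 0.85 = 80 per arm, 160 in total. The SAP's arithmetic is right. Expected unhealed subjects per arm: 68 × 0.045 = 3.1, or 80 × 0.045 = 3.6.

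**Step 2: operating characteristics.** The probability that the lower limit exceeds -10% was summed over all outcomes of the two binomials. Power is at 95.5% in both arms; one-sided error is at 85.5% test versus 95.5% control.

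| Interval | 68 per arm: power | error | 80 per arm: power | error |
|---|---|---|---|---|
| Wald (unpooled) | 82.0% | 4.0% | 85.4% | 3.8% |
| Agresti-Caffo | 75.3% | 3.0% | 83.0% | 2.8% |
| Newcombe | 66.8% | 2.2% | 77.5% | 2.5% |
| Miettinen-Nurminen | 66.8% | 2.2% | 72.9% | 2.1% |

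No row meets both targets at 68 (full 15% loss), nor at 80 (no loss). For the two intervals that hold the error, the power shortfall runs from 2.5 points (Newcombe, 80) to 13.2 points (either, 68).

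**Step 3: sensitivity.** Results move with n because the outcomes are discrete: Wald error is 3.3% to 4.3% over n = 64 to 80, and MN power is 66% to 74% over n = 68 to 80. At 68 per arm Wald error is 2.9%, 3.2% and 5.3% at control rates of 90%, 93% and 98%. MN error stays at or below 2.53% for control rates of 90% to 98.5% and n = 68 to 80.

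**Step 4: does the choice change verdicts?** With 95.5% in both arms, Wald passes and MN fails in 15.2% of trials at 68 per arm and 12.5% at 80; the reverse has probability zero. Examples (unhealed, test versus control):

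- 68 per arm, 4 versus 3. Wald: (64 - 65)/68 = -0.0147; standard error √(0.9412 × 0.0588/68 + 0.9559 × 0.0441/68) = 0.0379; lower limit -0.0147 - 1.96 × 0.0379 = -8.9%, pass. MN: -10.4%, fail.
- 80 per arm, 5 versus 3. Wald -9.2%, pass; MN -10.6%, fail.
- 80 per arm, 4 versus 2. Newcombe -9.9%, pass; MN -10.03%, fail.

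These outcomes lie close to what the SAP expects.

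**Step 5: size needed for 80% power with MN.** Power is 78.9% at 89 evaluable per arm and 82.1% at 90, and stays at or above 80% up to the 130 examined. 90 / 0.85 = 105.9, so 106 randomised per arm, 212 in total.

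**The case against.** The omission and the arithmetic are not in dispute. The best counter-arguments concern scope.

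*The figures are per evaluable subject, and the SAP does not say that dropouts leave the denominator.* This stands as a condition. If dropouts in an 80-per-arm full analysis set were counted as unhealed, the Wald/MN disagreement would fall to 6.7%, 1.5% and 1.2% at 5%, 10% and 15% loss. Power would fall much further, to 61%, 45% and 37% (Wald) or 54%, 43% and 36% (MN). The missing-data rule would then matter more than the interval. That is a further gap in the plan; it does not supply the missing interval.

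*The failure to meet both targets is local to the assumed rate.* True. At 96% in both arms with 80 evaluable, Newcombe gives 80.5% power and 2.48% error. At 98%, MN gives 82.8% power at 68 per arm with 1.9% error. In the other direction, MN power at 93% and 68 per arm is 55%. But 95.5% and 68 are the SAP's own planning values.

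*Wald against MN is the most divergent pair at 80 per arm.* Also true: there Wald and Newcombe disagree in 7.9% of trials, and Wald and Agresti-Caffo in 2.5%. Even Wald and MN agree in about 85% to 88%.

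*The unpooled formula points to Wald, and SAP 8 requires ethics committee approval for methods not specified.* A planning formula does not prespecify an analysis, and if Wald is meant, the 4.0% error remains. The approval clause is a weak safeguard, because any of these intervals satisfies an instruction to calculate a 95% interval.

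*MN is a preference.* Partly so. Newcombe also holds the error near 95.5% and has more power at 80 per arm. What matters is that one interval is named in advance.

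**Conclusion.** The concern holds. The interval for the only success criterion is unspecified throughout both documents. At the SAP's planning values, Wald reaches the stated power with about 4% one-sided error instead of 2.5%, while Newcombe and MN hold the error with about 67% power at 68 per arm (73% to 78% at 80). The choice alone changes the verdict in up to 15.2% of trials at 68 per arm and 12.5% at 80, always in the direction of Wald passing where MN fails.

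The sample size of 68 is not a slip; the gap comes from the normal approximation at rates near 100%. The sizes rest on equal true rates of 95.5%, on 68 to 80 evaluable subjects per arm with losses removed from the denominator, and on 2.5% one-sided error, which the documents imply but do not write. A test rate below 95.5% would lower the power further. This should be fixed before analysis.

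**What to change.** In SAP 5 and 7B, name one interval before the data are analysed. Suggested text: *the two-sided 95% Miettinen-Nurminen score interval for the difference in 24-week healing rate (test minus control) will be calculated; non-inferiority is concluded if its lower limit exceeds -10%.* If the sponsor prefers Newcombe, that is also defensible near these rates, but only one of the two may be named because they can disagree.

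In SAP 3, restate the power for the chosen interval at 95.5% in both arms. For MN this is about 67% with 68 evaluable per arm and about 73% with 80. Say that these figures assume subjects without a 24-week assessment are not in the denominator, or recompute them under whatever missing-data rule is adopted.

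The cost is one sentence in each of SAP 5, 7B and 3 and a standard software option; the sample size can stay at 160. The downside is a less favourable power statement. Keeping 80% power with MN is optional and not cheap: about 90 evaluable per arm, so 106 randomised per arm at 15% loss, or 212 in place of 160.
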